The general aim of this study is the development of the optimal algorithm for the management of all adnexal masses. This can be broken down into different specific objectives: 1) to study the occurrence of complications such as rupture, torsion, or malignancy in patients with benign looking conservatively treated masses; 2) to test the published IOTA diagnostic models for predicting that a mass is malignant at first visit or benign (either on the basis of histology following surgery or by the absence of malignant features on an ultrasound scan one year after the initial visit), and to predict complications (e.g. ocurrence of malignancy and other) during long-term follow-up; 3) to investigate factors that may be related to the need for surgery during long-term follow up; 4) to study the natural history of conservatively treated benign looking masses and to establish descriptive curves of the longitudinal changes seen in parameters from conservatively managed benign tumors (e.g. change in diameter, size of any solid component, number of papillations, or color score). We hope these curves will allow us to determine if any particular growth pattern is associated with complications or malignancy

Related to these four objectives, we aim to carry out the following analyses: 1) descriptive analysis of complications overall and by participating center (anonymised) and overall Kaplan-Meier curves for the need for surgery among benign looking masses; 2) estimation of discriminatory ability of LR1 for malignancy at the initial visit using the c-index and ROC curves and for complications during long-term follow-up using the hazard ratio and c-index within the context of survival analysis; 3) survival analysis to investigate predictors of the need for surgery during long-term follow-up of non-operated masses; 4) the development of longitudinal curves of the changes seen in the characteristics of non-operated masses using longitudinal analysis techniques such as mixed models and functional linear discriminant analysis (FLDA).

Methods

Study design

International multicenter prospective observational cohort study

Eligible for inclusion

- Any woman at least 18 years old with an adnexal mass.
- Any mass with benign ultrasound morphology may be suitable for conservative management.
- Pregnant patients can be included, but their data will be analysed separately.

Exclusion Criteria

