- If yes : date of first complication:

- And pop up list (you can select more than one):
 - Acute pain
 - \circ Chronic pain
 - Suspected torsion
 - o Infection
 - Haemorrhage
 - o Rupture
 - $\circ~$ Other, please specify:
- Death: date
- Death directly or indirectly relatd to adnexal mass?
- cause of death (

• Autopsy findings: specify:

Not needed for IOTA phase 5: second stage tests

Consent / information leaflet

Information leaflets are at the discretion of the participating centres. Approval of the local Ethical Committee for clinical studies is necessary.

Serum tumour markers

Serum CA 125 measurements or other tumour markers are performed locally, using a CA 125 II immunoradiometric assay

Tissue collection

Preferably the whole tumour should be removed. However, representative biopsies may be sufficient (e.g. in advanced ovarian cancer or endometrioma).

Tumour classification

Tumours are classified according to the criteria recommended by the International Federation of Gynecology and Obstetrics (FIGO). In malignant tumours the degree of differentiation is included.

Statistical analysis

For the first objective, a descriptive analysis of complications on all data and stratified for participating center (anonymized) will be performed, as well as an overall Kaplan-Meier curve of 'complication free survival'. Complication free survival is defined as the time to the need for surgery during long-term follow-up. Patients that did not need surgery at the end of the follow-up period are right censored at the time of the last examination.

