For the second objective, the discriminatory ability of LR1 and the polytomous model to detect malignancy at the initial visit will be assessed. To this end, the logit of the risk of malignancy given by LR1, logit(LR1), is used to predict malignancy using logistic regression, and the performance assessed with the odds ratio, the c-index and a ROC curve. Linearity of the effect of logit(LR1) will be assessed using spline functions. This analysis is planned one year after the end of the inclusion phase of the trial. Non-operated masses will be classified as benign at the initial visit if there is an absence of a clinical diagnosis of cancer after 1 year of follow up. In addition, the ability of LR1 to predict complications during long-term follow-up will be assessed. This will be done using Cox proportional hazards regression with the logit(LR1) as predictor of complication free survival. Performance will be assessed using the hazard ratio and the c-index within the context of survival analysis. Linearity of the effect of logit(LR1) will be investigated using Schoenfeld residuals.

For the third objective, a multivariable survival analysis will be undertaken using Cox proportional hazards regression or more complex alternatives based on support vector machines (30). The models will be penalized to prevent overfitting, given that not enough events (i.e., patients that need surgery during long term follow-up) are expected for the number of available predictor variables. Internal validation will be assessed through bootstrapping rather than a split of the data in training and test sets (31).

For the fourth objective, longitudinal normative curves will be derived of the changes seen in the characteristics of non-operated masses. Longitudinal analysis techniques such as mixed models, longitudinal support vector machines, and functional linear discriminant analysis (FLDA) (32-34).

Study supervision

Central supervision: the Steering Committee is responsible for the protocol, quality control, interim analyses of the data and final analysis and reporting of the study.

Local supervision: the Principal Investigators are responsible for the data collection in their centres.

[name] is responsible for the co-ordination of the overall IOTA project and the contact between the centres.

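### The protocol tests whether LR1 predicts long-term complications on an endpoint that counts need for surgery, which is the event of a different objective

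*Protocol*

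**What the plan says.** The protocol's Objectives section separates two questions. Objective 2 includes using the models "to predict complications (e.g. ocurrence of malignancy and other) during long-term follow-up", and the matching analysis assesses LR1 "for complications during long-term follow-up using the hazard ratio and c-index within the context of survival analysis". Objective 3 is about surgery, and its analysis is a "survival analysis to investigate predictors of the need for surgery during long-term follow-up of non-operated masses".

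The Statistical analysis section then fixes the endpoint under the first objective: "Complication free survival is defined as the time to the need for surgery during long-term follow-up". It adds: "Patients that did not need surgery at the end of the follow-up period are right censored at the time of the last examination". Under the second objective, the long-term LR1 analysis is a Cox regression "with the logit(LR1) as predictor of complication free survival". Under the third objective, the penalised models are justified because "not enough events (i.e., patients that need surgery during long term follow-up) are expected for the number of available predictor variables".

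Need for surgery is not defined anywhere. The follow-up form (Recorded variables) has a yes/no field for complications of the mass, a date for the first one, and a list: acute or chronic pain, suspected torsion, infection, haemorrhage, rupture, other. The operation form lists indications, including ultrasound suspicion, patient request, fertility concerns and incidental removal during another operation. Its list of findings includes an entry for no tumour complication.

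**The concern.** The analysis meant to show whether LR1 predicts complications uses the same event as the analysis of who comes to surgery. On the study's own forms these are different events, and they can diverge in both directions.

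The protocol intends to build decision aids on surgery and follow-up. A hazard ratio and c-index reported as LR1's prediction of complications would in fact describe LR1's relation to operations judged necessary. Some of the listed indications (ultrasound suspicion, growth, change in morphology) are related to LR1's ultrasound variables, although they are not the same thing. A real association with complications could be diluted, or an association with the decision to operate could be reported as prediction of complications.

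**Working it through.** **Step 1. Which event each analysis uses.**

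| Analysis | Stated target | Event used |
|---|---|---|
| Objective 1, curve | Need for surgery (Objectives); complication free survival (Statistical analysis) | Need for surgery |
| Objective 2, first visit | Malignancy | Malignancy, a separate outcome |
| Objective 2, long term | Complications | Need for surgery |
| Objective 3 | Need for surgery | Need for surgery |

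Target and event differ in the third row. In the first row only the label is wrong.

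**Step 2. How the forms let the two events diverge.**

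- *Complication, no surgery needed.* Suspected torsion, infection, haemorrhage or rupture recorded at a follow-up visit is dated on the form. If surgery was not needed, the censoring rule treats the woman as event free. This holds however need is read.
- *Surgery, no complication.* An operation prompted by ultrasound suspicion that finds no tumour complication can count as needed, so it can be an event. Patient-request and incidental removals count only if need is read broadly.

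**Step 3. Possible size.** The protocol gives no event count, power or expected event mix, so there is no planned figure to reproduce. Every input below is assumed.

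*Surgery without a complication counted.* Compare high with low LR1. Let f be the share of surgery in the low group that is due to a complication, HRc the hazard ratio for that surgery, and HRo the hazard ratio for other surgery. Cause-specific hazards add, so at baseline:

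apparent HR = f × HRc + (1 − f) × HRo

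| HRc (true) | HRo | f = 10% | f = 30% | f = 50% | f = 100% |
|---|---|---|---|---|---|
| 2.0 | 1.0 | 1.10 | 1.30 | 1.50 | 2.00 |
| 1.0 | 2.0 | 1.90 | 1.70 | 1.50 | 1.00 |
| 2.0 | 2.0 | 2.00 | 2.00 | 2.00 | 2.00 |

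Example, first row at f = 30%: 0.3 × 2.0 + 0.7 × 1.0 = 1.30.

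I also simulated Cox models with a standardised continuous logit(LR1), hazard ratios per SD, 60,000 patients per setting and five years of follow-up. Baseline hazards were set to give 20% surgery at average LR1. For the same values of f, the first row gave 1.08, 1.26, 1.46 and 2.02. The second gave 1.87, 1.66, 1.46 and 1.02. The third gave 1.99 to 2.00. A cause-specific Cox model for complications alone recovered the true value in every setting (1.97 to 2.02 for 2.0; 0.99 to 1.04 for 1.0).

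*Only surgery with a complication counted.* Let s be the share of complications in the low group that do not lead to surgery. The hazard ratio for all complications is then (1 − s) × HR(operated) + s × HR(unoperated). With 2.0 and 1.0, and s = 10, 25 or 50%, it is 1.90, 1.75 or 1.50, while the analysis as written gives 2.0. With 1.0 and 2.0 it is 1.10, 1.25 or 1.50, against 1.0 as written. With equal ratios there is no bias.

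**The case against.** Five points can be made for the plan.

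1. *The curve is openly about surgery.* The Objectives section announces "overall Kaplan-Meier curves for the need for surgery among benign looking masses", and the Statistical analysis section also plans a descriptive analysis of complications. The 2017 SAP goes further, with competing-risk cumulative incidence of surgery, resolution and death, and surgery divided by reason and finding (Follow-up study, section 1.2.2 and Box 1). This stands. For the Kaplan-Meier curve the fault is mainly its name. One limit remains: the SAP counts complications only as findings at surgery.

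2. *Need implies medical need.* Patient-request and incidental removals are hard to call needed. This is fair, and a reader should not infer that all elective surgery counts, since the text does not settle it. The narrow reading still admits operations for suspicion that find nothing, and it still censors complications managed without surgery.

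3. *The protocol treats required surgery as a complication.* It appears in the list of complications during pregnancy (Collection of clinical data). That makes surgery one kind of complication, in one subgroup. It does not make it the definition of all complications.

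4. *Malignancy will usually lead to surgery.* That is plausible, and the component would then be largely captured. It would still be pooled with surgery for every other reason.

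5. *The SAP may have moved on.* Its follow-up part contains no LR1 analysis, and its model part lists LR2 rather than LR1 and has benign or malignant status as outcome (section 1.4). Both parts are headed as interim. They neither repair nor withdraw the protocol's long-term LR1 analysis, and no final-analysis plan is among the documents.

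**Conclusion.** The point holds for one analysis, the long-term complication part of objective 2. As written, its hazard ratio and c-index do not estimate LR1's prediction of complications. This follows from the protocol's wording and needs no outside assumption.

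The size and direction of the bias are unknown, because the documents give neither the share of operations that involve a complication nor the share of complications that do not lead to surgery. The figures above show only what is possible: overstatement if LR1 relates mainly to other surgery, understatement if it relates mainly to complications, and none if the relations are equal.

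Two stronger readings are tempting. One is that LR1 will look better than it is. The documents do not support any direction. The other is that the study's complication results as a whole are unsound. They do not support that either: LR1 for malignancy at the first visit has its own outcome, and the descriptive complication analysis does not depend on this endpoint.

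This should be corrected before the long-term LR1 analysis is run.

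**What to change.** 1. Rename the present endpoint time to surgery, state which surgery counts, and keep it for objective 3 and for the curve announced in the Objectives section.

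2. For the long-term LR1 analysis, define the event as the first complication, being the earliest of:
   - malignancy, by histology or by clinical diagnosis without surgery;
   - torsion, rupture, bleeding or infection found at surgery;
   - suspected torsion, rupture, haemorrhage or infection recorded at follow-up, with its date;
   - death recorded as related to the mass.

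   Where an operation was done for any such recorded complication, apply one stated rule to all of them on whether the operative finding decides. State whether pain and adhesions count, and show results both ways. Keep pregnancy and delivery complications in the separate analysis of pregnant patients that the protocol already plans.

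3. Fit a cause-specific Cox model for logit(LR1), with surgery without a complication, spontaneous resolution and unrelated death as competing events.

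**Cost.** This needs new wording and one derived variable, almost entirely from fields already collected. There may be fewer events. If every complication is operated on and a share p of operations involve one, the standard error of the log hazard ratio rises by about 1/√p: 3.2, 1.8 or 1.4 times at an assumed p of 10, 30 or 50%. Unoperated events rest on clinical judgement. Dating is incomplete, because the form dates only the first complication and has no dedicated dated field for cancer diagnosed without surgery. These limits should be stated with the results.

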In this international multicentre study IOTA phase 5 we aim to develop the optimal evidence-based algorithm for the management of all adnexal tumours in order to improve the detection of ovarian cancer while at the same time reducing the number of unnecessary operations. At least three thousand patients with an adnexal mass will undergo an ultrasound examination and if no operation is needed they will be followed up for at least 5 years. At each visit the investigator will assess the tumour and decide whether surgery is necessary based on the available information and local protocols. Survival and logistic regression analysis will be used to develop decision aids to assist clinicians in making decisions regarding surgery and follow up.

Relation with other IOTA studies

The **IOTA study (International Ovarian Tumour Analysis)** is a multicentre collaborative project for the pre-operative characterisation of ovarian tumours..

IOTA phase 1: The **first phase** of IOTA was conducted between 1999 and 2002. Several new mathematical models were developed based on the prospectively collected data of 1066 patients with a persisting adnexal tumour from 9 European centres (1). Between 2002 and 2005 three centres continued the prospective collection in order to be able to perform an internal validation of mathematical models developed in IOTA phase 1. In this so-called IOTA **phase 1b** study a dataset of 507 new patients was prospectively collected in 3 out of the 9 original IOTA centres (2). All models proved to perform excellently with areas under the ROC curves of more than 0.94.

IOTA phase 2: The **second phase** of IOTA consisted of an external validation of the models and this was conducted between 2005 and 2007. The diagnostic algorithms were prospectively validated on 1938 patients with adnexal tumours in 19 centres in Belgium, Italy, UK, Sweden, Poland, Czech Republic, Canada, and China (3). A first analysis showed that overall performance of the logistic regression models was excellent (area under the ROC curve 0.94). We concluded that a subgroup of "uncertain" tumours needs a reliable second stage test in order to help even experienced ultrasound examiners.

IOTA phase 3: The third phase of the IOTA study started in 2010.

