1.2.2 Methods

To describe findings during follow up, we will use cumulative incidence curves that reflect the competing risk setting. The follow-up time will be computed in months.

In competing risk survival analysis, the hazard and cumulative incidence of competing (i.e. mutually exclusive) events are estimated over time. The basic competing risk outcome levels reflect the overall study outcome, and are 'surgery performed', 'cyst spontaneously resolved', and 'patient died (for any reason)', whichever comes first. When surgery is performed, this can be further subdivided based on reason for surgery and findings at surgery. For these subdivisions, it is possible that two events (i.e. reasons or findings) occur simultaneously. For example, a patient can undergo surgery due to acute pain and fertility concerns. We therefore specified a hierarchy of the competing events and if two events occur simultaneously, the event highest in the hierarchy is given to the observation. The hierarchies are shown in Box 1. For example, when the patient is operated due to acute pain and fertility concerns, the patient is said to have the event acute pain.

Box 1. Hierarchy of reasons for surgery and findings at surgery.

Reasons for surgery	Findings at surgery
1. Suspicion of malignancy ^a	1. Invasive
2. Pain ^b	2. Borderline
3. Patient request/opportunistic ^c	3. Torsion
	4. Cyst rupture
	5. Minor complications ^d
	6. No complications of tumor

^a Includes ‘suspicion of malignancy based on ultrasound; suspicion of malignancy based on: increase in size, change in morphology, change in vascularity, raised or increase in CA125, raised HE4, CT finding, MRI findings’

^b Includes ‘acute pain (suspected torsion, suspected cyst rupture), chronic pain’

^c Includes ‘fertility concerns, patient request, opportunistic removal’

^d Includes ‘tumor bleeding, adhesions, inflammation/infection’

We will derive cumulative incidence functions for study outcome, reason for surgery, and findings at surgery. For each outcome, figures depicting the cumulative incidence will be produced, as well as tables at time points 12 and 24 months containing the cumulative incidences of the competing events with 95% CI.

Median follow-up will be estimated by the reverse Kaplan-Meier method, i.e. where censoring is denoted as the event, and events denoted as censoring. This is the common method to visualize the censoring function.

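### The protocol's long-term Kaplan-Meier curve of time to surgery has no competing-risk treatment of spontaneous resolution or death, although the interim SAP provides one

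*Protocol*

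**What the plan says.** **Protocol, Statistical analysis, first objective.** A Kaplan-Meier curve is planned for an endpoint named complication free survival: "Complication free survival is defined as the time to the need for surgery during long-term follow-up". The censoring rule is: "Patients that did not need surgery at the end of the follow-up period are right censored at the time of the last examination". Neither resolution nor death is mentioned.

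**Protocol, Statistical analysis, second and third objectives.** The long-term performance of LR1 is assessed "using Cox proportional hazards regression with the logit(LR1) as predictor of complication free survival". The outputs are named: "Performance will be assessed using the hazard ratio and the c-index within the context of survival analysis". The third objective is a multivariable Cox model, or a support vector alternative, with surgery as the event.

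**Protocol, opening summary.** "Survival and logistic regression analysis will be used to develop decision aids". The form of output from these aids is not specified.

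**Protocol, recorded variables.** Spontaneous resolution is an entry on the ultrasound screen. Death is recorded with its date.

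**Protocol, number of study patients and recruitment period.** Follow-up lasts at least 5 years, and surgery is the only exception named there.

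**SAP, follow-up study, section 1.2.2.** Findings are described by "cumulative incidence curves that reflect the competing risk setting". Surgery, resolution and death from any cause are the competing outcomes, and the first to occur counts. Section 1.1 limits displayed results to 30 months because later follow-up is incomplete. The document is headed as an interim analysis. The second SAP concerns diagnosis at inclusion and does not cover time to surgery.

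**The concern.** A mass that has resolved, or a woman who has died, can no longer lead to surgery for that mass. Kaplan-Meier treats a censored woman as having the same future surgery hazard as those still at risk. Where resolution or death is what ends her observation, that is untrue, and one minus Kaplan-Meier no longer estimates the proportion of women who will have surgery.

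The study aims to inform the choice between surgery and conservative follow-up. An inflated 5-year probability of surgery would make conservative management look less durable than it is. The sponsor's own SAP recognises the problem, but its solution reaches only the interim curves. Neither SAP covers the 5-year curve or the two long-term Cox analyses, so the protocol's Statistical analysis section is the only text supplied for them.

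**Working it through.** The documents give no surgery, resolution or death rate and no sample size calculation, so there is no figure in the plan to reproduce. All rates below are assumptions.

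**Direction.** Let h_s be the cause-specific hazard of surgery and h_c that of resolution plus death, with S_s(t) and S_c(t) the survival functions each hazard would give alone.

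- True cumulative incidence: CIF(t) = ∫ h_s(u) S_s(u) S_c(u) du.
- Kaplan-Meier with exit at the competing event targets: 1 − S_s(t) = ∫ h_s(u) S_s(u) du.

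Since S_c ≤ 1, the second is never smaller than the first. It is strictly larger if any competing event precedes later surgery in the cohort. This needs no constant-hazard assumption.

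**Size under constant hazards.** Assume 24-month surgery of 16% and resolution of 20%, with women leaving the risk set at resolution.

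1. Total hazard = −ln(1 − 0.16 − 0.20)/24 = 0.4463/24 = 0.01860 per month.
2. h_s = 0.01860 × 16/36 = 0.00826; h_c = 0.01860 × 20/36 = 0.01033.
3. At 24 months: 1 − KM = 1 − exp(−0.1983) = 18.0%, against a CIF of 16.0%.
4. At 60 months: 1 − KM = 1 − exp(−0.4959) = 39.1%. CIF = (16/36) × (1 − exp(−1.1157)) = 0.4444 × 0.6723 = 29.9%. The gap is 9.2 points.

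**Range at 60 months, same formulas:**

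| Assumed 24-month competing events / surgery | CIF | 1 − KM | Ratio |
|---|---|---|---|
| 1% / 15% | 33.1% | 33.5% | 1.01 |
| 10% / 15% | 30.8% | 35.0% | 1.14 |
| 20% / 10% | 19.7% | 25.7% | 1.31 |
| 20% / 16% | 29.9% | 39.1% | 1.31 |
| 30% / 16% | 27.3% | 41.5% | 1.52 |
| 40% / 15% | 23.6% | 42.0% | 1.78 |

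**If rates fall off after 24 months (20%/16% case).**

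- No resolution after 24 months, surgery hazard unchanged: CIF = 0.16 + 0.64 × (1 − exp(−0.00826 × 36)) = 32.5%. One minus Kaplan-Meier stays at 39.1%, so the gap is 6.6 points.
- No surgery after 24 months: the values stay at 18.0% and 16.0%, a gap of 2.0 points.

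**If resolved women stay under scan.** With no censoring before 60 months, Kaplan-Meier reduces to the simple proportion not operated on, so 1 − KM equals the CIF. A simulation of 200,000 women with assumed 24-month surgery of 15% and competing events of 20% shows this. At 60 months, 1 − KM is 28.3% if all resolved women stay under scan (equal to the CIF), 31.8% if half leave at resolution, and 37.0% if all leave.

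**The case against.** **The protocol never says that resolved masses are censored at resolution.** This stands. A reader might infer it from the rule about the last examination, but the protocol names only surgery as an exception to 5 years of follow-up. If resolved women are scanned throughout, resolution causes no bias. Some SAP text suggests that resolution ends the story: it is a final study outcome, and a resolved case counts as having useful information without a minimum follow-up. SAP section 1.1 also reports considerable differences between centres in adherence to follow-up. That makes the handling unclear; it does not establish exit at resolution. Death is different, because a woman who dies is necessarily censored at her last scan.

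**The Cox analyses are not wrong.** This also stands. A reader might infer that they share the bias. Censoring competing events gives a valid cause-specific hazard ratio, and the second objective reports only the hazard ratio and c-index. The third looks for factors related to surgery, for which a cause-specific model is a standard choice. The problem arises only if these models are turned into absolute risks without the competing hazards. The decision aids might do that, but the protocol does not say so.

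**The sponsor already uses the right method.** True for the interim analysis. The absence of a 5-year plan from an interim SAP does not show that the sponsor will return to Kaplan-Meier. But no document supplied says that the competing-risk approach carries over.

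**The c-index is a matter of estimand.** Keeping resolved masses as event-free targets cumulative incidence, while censoring them targets the cause-specific hazard. The protocol does not say which is meant, so this needs a statement and is not an error.

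**Conclusion.** The point holds for the long-term Kaplan-Meier curve and for any absolute risk built from the Cox models. The protocol has no competing-risk treatment of two events that it records and that the SAP treats as competing. The direction is certain whenever women leave the risk set at resolution or death before later surgery occurs. The size is unknown.

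The 9.2-point gap at 60 months is an illustration, not an estimate. It rests on assumed 24-month rates, constant hazards carried to 60 months, and exit at resolution. Relax these and the gap shrinks, to zero for resolution if resolved women remain under scan. With a competing incidence of only 1% at 24 months, the excess at 60 months is about 1% in relative terms. The gap in the plan is worth closing, but it does not invalidate the planned hazard ratios.

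**What to change.** In the protocol or a long-term SAP:

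1. Replace one minus Kaplan-Meier for time to surgery with the cumulative incidence approach of section 1.2.2 of the follow-up SAP, with resolution and death as competing events, over the full follow-up.
2. Label the Cox hazard ratios of the second and third objectives as cause-specific.
3. For any absolute risk used in the decision aids, combine the cause-specific hazards for surgery, resolution and death.
4. State how resolved masses and deaths are handled in the analysis, including the c-index, so that it matches the quantity intended.

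The cost is revised wording and a small amount of extra analysis on data already collected. The cumulative incidence curves use a method the SAP already plans. The combined absolute risks and any competing-risk c-index would be new, because the SAP plans only descriptive incidence.
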